### **14.1 Protocol amendments**

Any change or addition to the protocol can only be made in a written protocol amendment that must be approved by Novartis, health authorities where required, and the IRB/IEC prior to implementation.

Only amendments that are required for participant safety may be implemented immediately provided the health authorities are subsequently notified by protocol amendment and the reviewing IRB/IEC is notified.

Notwithstanding the need for approval of formal protocol amendments, the investigator is expected to take any immediate action required for the safety of any participant included in this study, even if this action represents a deviation from the protocol. In such cases, Novartis should be notified of this action and the IRB/IEC at the study site should be informed according to local regulations.

## 16 Appendices

### 16.1 Appendix 1: Neurological Symptoms or Signs

New neurological findings are defined as clinical signs or symptoms that raise concern in respect to neurological conditions. They include but are not limited to:

- Significant new or worsening neurological symptoms or signs, as reported spontaneously by the participants/study partners at any time, or detected during the scheduled physical/neurological examinations, including but not limited to new or worsening peripheral neuropathies, visual disturbances or seizures
- Worsening of cognition not consistent with the previous clinical course, as reported spontaneously by the participants/study partners at any time or observed at the clinical assessments (e.g. NTB, NPI)

Investigators will be asked to review the finding and initiate any additional tests as needed. Summary of the findings will be provided to the Safety Monitor, regardless of the suspected relationship to investigational drug.

## 16.2 Appendix 2: Liver event and Laboratory trigger Definitions and Follow-up Requirements

**Table 16-1 Liver event and laboratory trigger definitions**

	Definition/ threshold
Liver laboratory triggers If ALT, AST and total bilirubin normal at baseline:	

ALT or AST <math>> 5 \times</math> ULN

ALP <math>> 2 \times</math> ULN (in the absence of known bone pathology)

TBL <math>> 3 \times</math> ULN (in the absence of known Gilbert syndrome)

ALT or AST <math>> 3 \times</math> ULN and INR <math>> 1.5</math>

Potential Hy's Law cases (defined as ALT or AST <math>> 3 \times</math> ULN and TBL <math>> 2 \times</math> ULN [mainly conjugated fraction] without notable increase in ALP to <math>> 2 \times</math> ULN)

Any clinical event of jaundice (or equivalent term)

ALT or AST <math>> 3 \times</math> ULN accompanied by (general) malaise, fatigue, abdominal pain, nausea, or vomiting, or rash with eosinophilia

Any adverse event potentially indicative of a liver toxicity*

If ALT or AST abnormal at baseline	

ALT or AST <math>> 3 \times</math> baseline or <math>> 300</math> U/L (whichever occurs first)

\*These events cover the following: Hepatic failure, fibrosis and cirrhosis, and other liver damage-related conditions; the non-infectious hepatitis; the benign, malignant and unspecified liver neoplasms TBL: total bilirubin; ULN: upper limit of normal

**Table 16-2 Follow up requirements for liver laboratory triggers – ALT, AST, TBL**

ALT	TBL	Liver Symptoms	Action
ALT increase without bilirubin increase:			
If normal at baseline: ALT > 3 x ULN	Normal For patients with Gilbert's syndrome: No change in baseline TBL	None	
 
• No change to study treatment
 

If elevated at baseline: ALT > 2 x baseline or > 300 U/L (whichever occurs first)			
 
• Measure ALT, AST, ALP, GGT, TBIL, INR, albumin, CK, and GLDH in 48-72 hours.
 
• Follow-up for symptoms.
 

ALT increase with bilirubin increase:			
If normal at baseline: ALT > 8 x ULN	Normal	None	
 
• Follow-up for symptoms.
 
• Initiate close monitoring and workup for competing etiologies.
 

If normal at baseline: ALT > 3 x ULN	TBL > 2 x ULN (or INR > 1.5) For patients with Gilbert's syndrome: Doubling of direct bilirubin	None	
 
• Study drug can be restarted only if another etiology is identified and liver enzymes return to baseline.
 

If elevated at baseline: ALT > 2 x baseline or > 300 U/L (whichever occurs first)			
If normal at baseline: ALT > 3 x ULN	Normal or elevated	Severe fatigue, nausea, vomiting, right upper quadrant pain	
If elevated at baseline:			

ALT	TBL	Liver Symptoms	Action
ALT > 2 x baseline or > 300 U/L (whichever occurs first)			

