## 10.2 Additional Safety Monitoring

### 10.2.1 Liver safety monitoring

To ensure participant safety and enhance reliability in determining the hepatotoxic potential of an investigational drug, a standardized process for identification, monitoring and evaluation of liver events has to be followed.

Please refer to [Table 16-1](#) in [Section 16](#) for complete definitions of liver laboratory triggers and liver events.

Once a participant is exposed to study treatment, every liver event defined in [Table 16-1](#) should be followed up by the investigator or designated personnel at the trial site, as summarized below. Additional details on actions required in case of liver events are outlined in [Table 16-2](#). Repeat liver chemistry tests (i.e., ALT, AST, TBL, PT/INR, ALP and G-GT) to confirm elevation.

- These liver chemistry repeats will be performed using the central laboratory. If results will not be available from the central laboratory, then the repeats can also be performed at a local laboratory to monitor the safety of the participant. If a liver event is subsequently

reported, any local liver chemistry tests previously conducted that are associated with this event should have results recorded on the appropriate CRF.

- If the initial elevation is confirmed, close observation of the participant will be initiated, including consideration of treatment interruption if deemed appropriate.
- Discontinuation of the investigational drug (see Discontinuation of Study Treatment [Section 9.1.1](#)), if appropriate
- Hospitalization of the participant if appropriate
- Causality assessment of the liver event
- Thorough follow-up of the liver event should include:
  - Repeating liver chemistry tests two or three times weekly. Testing should include ALT, AST, ALP, PT/INR, and GGT. If total bilirubin is elevated  $> 2 \times$  ULN, fractionation into direct and indirect bilirubin is required. To rule out muscular origin or transaminase elevations, CPK should be measured along with liver chemistry tests. Frequency of retesting can decrease to once a week or less if abnormalities stabilize or the study drug has been discontinued and the participant is asymptomatic. Retesting should be continued up to resolution.
  - Obtaining a more detailed history of symptoms and prior or concurrent diseases.

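### Tables 16-1 and 16-2 do not map to each other: liver events are defined on ALT or AST with a broad symptom list, but the action rows use ALT only and a shorter list

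*Protocol*

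**What the plan says.** Protocol Table 16-1 (Appendix 2, Section 16.2) defines the liver events. For participants with normal baseline values, its transaminase triggers all apply to either enzyme: above 5 x ULN; above 3 x ULN with INR above 1.5; "Potential Hy's Law cases (defined as ALT or AST" above 3 x ULN with total bilirubin (TBL) above 2 x ULN, mainly conjugated and without a notable ALP rise); and above 3 x ULN "accompanied by (general) malaise, fatigue, abdominal pain, nausea, or vomiting, or rash with eosinophilia".

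Section 10.2.1 asks for follow-up of every event in that table and adds: "Additional details on actions required in case of liver events are outlined in" Table 16-2. Section 9.1.1 takes liver events out of its rule for severe related adverse events and sends the decision on stopping treatment to Section 16.2.

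Table 16-2 is titled "Follow up requirements for liver laboratory triggers – ALT, AST, TBL". Its first block is headed "ALT increase without bilirubin increase". Each row is entered through an ALT value; AST appears only among the tests to repeat. The symptom column has two entries: *None*, and "Severe fatigue, nausea, vomiting, right upper quadrant pain". For ALT above 3 x ULN, normal TBL and symptoms *None*, the action is "No change to study treatment", with repeat tests in 48 to 72 hours and follow-up for symptoms. The next row with normal TBL and no symptoms starts at ALT above 8 x ULN.

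Table 16-3 covers isolated hyperbilirubinemia. It ends with a general row for adverse events that may indicate liver toxicity, under which interruption or discontinuation is to be considered.

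**The concern.** A site identifies a liver event from one table and looks up what to do in the other. If the second table uses fewer enzymes and fewer symptoms, some defined events cannot be looked up, and two sites can treat the same presentation differently. Because Section 9.1.1 relies on Section 16.2 for the discontinuation decision, the gap falls where the protocol meant to be explicit.

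There is also a consequence for the data. Section 9.1.1 treats a participant who stops study treatment as discontinued from the study and calls that participant to an Early Termination Visit, so the scheduled week-24 NTB would not be collected. Uneven handling of liver events could therefore affect who contributes the primary endpoint. Neither document gives event rates from which to size this.

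**Working it through.** No sample size, power or alpha figure is involved. The check sets the two tables side by side for participants with normal baseline values.

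**Enzyme.** Table 16-1 has four transaminase triggers that AST alone can meet: above 5 x ULN, and above 3 x ULN with raised INR, with raised TBL, or with symptoms. Table 16-2 needs ALT above 3 x ULN for entry to any row. With ALT at or below 3 x ULN, 0 of the 4 AST triggers match a row.

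**Symptoms.** Table 16-1 has six symptom groups. If *severe* in Table 16-2 qualifies fatigue only, two match fully (nausea, vomiting), two match in part (fatigue if severe, abdominal pain if right upper quadrant) and two never match (malaise, rash with eosinophilia). If *severe* qualifies the whole list, none matches fully, four match in part and two never match.

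**Cases.** Values are multiples of ULN except INR; anything not mentioned is normal. *Strict* reads the entry *None* as no symptom at all. *Loose* reads it as none of the symptoms that Table 16-2 lists. Every case is a Table 16-1 event.

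| Case | Table 16-2, strict | Table 16-2, loose |
|---|---|---|
| ALT 4, malaise | no row | no-change row |
| ALT 4, non-severe fatigue | no row | no-change row |
| ALT 4, abdominal pain not right upper quadrant | no row | no-change row |
| ALT 4, rash with eosinophilia | no row | no-change row |
| ALT 4, nausea | symptom row | symptom row |
| AST 6, ALT 2 | no row | no row |
| AST 4, ALT 2, TBL 2.5 (mainly conjugated, ALP not above 2) | no row | no row |
| AST 4, ALT 2, INR 1.6 | no row | no row |
| AST 4, ALT 2, nausea | no row | no row |
| AST 6, ALT 4 | no-change row | no-change row |
| ALT 6 alone | no-change row | no-change row |

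The cases were chosen to probe the tables, so their counts are not frequencies. Three results follow.

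1. The AST gap does not depend on how *None* is read. The same combinations with ALT at 4 in place of AST (TBL 2.5, INR 1.6, or nausea) each have a row; with AST they have none.
2. The symptom gap does depend on it: the four unlisted-symptom cases move from no row to the no-change row.
3. With AST 6 and ALT 4, the ALT value alone selects the row; the AST value that made it an event above 5 x ULN plays no part.

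**Table 16-3.** A TBL of 2.5 x ULN lies within its lowest band, but that band is for an isolated rise. Raised TBL with AST above 3 x ULN is not isolated, so Table 16-3 does not cover the AST form of potential Hy's Law as a hepatocellular event.

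**The case against.** The strongest reply is that no participant is left without follow-up. Section 10.2.1 applies to every Table 16-1 event, whichever enzyme or symptom produced it. It calls for repeat liver tests and, once the elevation is confirmed, "close observation of the participant will be initiated, including consideration of treatment interruption if deemed appropriate". It also provides for discontinuation or hospitalization if appropriate, causality assessment, and retesting two or three times weekly. It cites Table 16-2 for further detail only. The last row of Table 16-3 is a catch-all, and Section 9.1.1 requires stopping when the investigator believes continuation would harm the participant. A liver event guide in the Site Operations Manual may say more, but it is not among the documents. All of this stands and limits the point. These provisions rest on judgement, however, and do not supply the missing rows.

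Two stronger inferences are tempting. A reader might infer that an AST Hy's Law case is told to stay on treatment by the lowest TBL band of Table 16-3; the table's restriction to isolated hyperbilirubinemia rules that out. A reader might also infer that the no-change instruction contradicts Table 16-1 whenever it meets a defined event. It does not: Table 16-1 says what must be followed up, not that treatment must change, and ALT of 6 x ULN alone is a defined event that receives the no-change row with retesting. For the unlisted-symptom cases, that row applies only on the loose reading of *None*.

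Table 16-2 is also visibly damaged in the available text, and action cells may be merged or lost. Nothing here is concluded from empty action cells; the ALT criteria and the symptom list are legible. Finally, the SAP (Section 1.1) reports termination after 34 of about 86 planned participants were randomized, which lowers the urgency for Cohort 1. Section 16 belongs to the core text that Section 4.1 carries forward across cohorts, so a later cohort would inherit the mismatch.

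**Conclusion.** The concern holds as an internal inconsistency between the definition table and the action table. With ALT at or below 3 x ULN, all four AST-driven triggers lack a Table 16-2 row. Of the six symptom groups, two never match and at least two match only in part. With ALT between 3 and 8 x ULN and normal TBL, an unlisted symptom leaves either no row or the no-change row, depending on the reading of *None*, so sites may differ.

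The conclusion assumes normal baseline values and relies on the legible row criteria, not on the action cells. It does not show that any participant would go unmonitored, that dosing would wrongly continue, or that the week-24 result would be biased. The documents give no frequency for AST-only or unlisted-symptom events. The correction is worth making because the tables govern a safety decision and the change is small.

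**What to change.** Reconcile Tables 16-1 and 16-2: one symptom list, consistent ALT/AST wording, and each transaminase trigger in Table 16-1 leading to one action row. State what the symptom entry *None* means. The sponsor's hepatic-safety function decides which list, thresholds and actions apply; this review takes no view on them. The same edit should settle a neighbouring mismatch for abnormal baseline values, where Table 16-1 uses above 3 x baseline for ALT or AST and Table 16-2 uses above 2 x baseline for ALT; both also give 300 U/L.

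The cost is an edit to one appendix, by amendment before any further cohort opens. It needs no new tests, visits or participants.

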**Table 16-3 Follow up requirements for liver laboratory triggers – Isolated Hyperbilirubinemia**

Criteria	Actions required	Follow-up monitoring
Total Bilirubin (isolated)		
>1.5 – 3.0 x ULN	
 
Maintain treatment
 
Repeat LFTs within 48-72 hours
 
	Monitor LFTs weekly until resolution to ≤ Grade 1 or to baseline
> 3 - 10 x ULN (in the absence of known Gilbert syndrome)	
 
Interrupt treatment
 
Repeat LFT within 48-72 hours
 
Hospitalize if clinically appropriate
 
Establish causality
 
Record the AE and contributing factors (e.g. conmeds, med hx, lab) in the appropriate CRF
 
	Monitor LFTs weekly until resolution to ≤ Grade 1 or to baseline (ALT, AST, total bilirubin, Alb, PT/INR, ALP and GGT) Test for hemolysis (e.g. reticulocytes, haptoglobin, unconjugated [indirect] bilirubin)
> 10 x ULN	
 
Discontinue the study treatment immediately
 
Hospitalize the participant
 
Establish causality
 
Record the AE and contributing factors(e.g. conmeds, med hx, lab)in the appropriate CRF
 
	ALT, AST, total bilirubin, Alb, PT/INR, ALP and GGT until resolution (frequency at investigator discretion)
Any AE potentially indicative of a liver toxicity	
 
Consider study treatment interruption or discontinuation
 
Hospitalization if clinically appropriate
 
Establish causality
 
Record the AE and contributing factors(e.g., conmeds, med hx, lab)in the appropriate CRF
 
	Investigator discretion

Based on investigator's discretion investigation(s) for contributing factors for the liver event can include: Serology tests, imaging and pathology assessments, hepatologist's consultancy; obtaining more detailed history of symptoms and prior or concurrent diseases, history of concomitant drug use, exclusion of underlying liver disease.

**Table 16-4      Exclusion of Underlying Liver Disease**

Disease	Assessment
Hepatitis A, B, C, E	IgM anti-HAV; HBSAg, IgM anti-HBc, HBV DNA; anti-HCV, HCV RNA, IgM & IgG anti-HEV, HEV RNA
CMV, HSV, EBV infection	IgM & IgG anti-CMV, IgM & IgG anti-HSV; IgM & IgG anti-EBV
Autoimmune hepatitis	ANA & ASMA titers, total IgM, IgG, IgE, IgA
Alcoholic hepatitis	Ethanol history, gGT, MCV, CD-transferrin
Nonalcoholic hepatitis	Ultrasound or MRI
Hypoxic/ischemic hepatopathy	Medical history: acute or chronic CHF, hypotension, hypoxia, hepatic venous occlusion Ultrasound or MRI
Biliary tract disease	Ultrasound or MRI, ERCP as appropriate
Wilson disease	Caeruloplasmin
Hemochromatosis	Ferritin, transferrin
Alpha-1-antitrypsin deficiency	Alpha-1-antitrypsin

## 16.3 Appendix 3: Specific Renal Alert Criteria and Actions and Event Follow-up

**Table 16-5 Specific Renal Alert Criteria and Actions and Event Follow-up**

Renal Event	Actions
Confirmed serum creatinine increase 25 – 49%	
 
Consider causes and possible interventions
 
Follow up within 2-5 days
 

Serum creatinine increase  50 % + OR if <18 years old, eGFR 35 mL/min/1.73 m 	
 
Consider causes and possible interventions
 
Repeat assessment within 24-48h if possible
 
Consider drug interruption or discontinuation unless other causes are diagnosed and corrected
 
Consider participant hospitalization and specialized treatment
 

New onset dipstick proteinuria ≥ 3+ OR Protein-creatinine ratio (PCR) ≥ 1g/g Cr (or mg/mmol equivalent as converted by the measuring laboratory)	
 
Consider causes and possible interventions
 
Assess serum albumin & serum total protein
 
Repeat assessment to confirm
 
Consider drug interruption or discontinuation unless other causes are diagnosed and corrected
 

New onset hematuria ≥ 3+ on urine dipstick	
 
Repeat assessment to confirm
 
Distinguish hemoglobinuria from hematuria
 
Urine sediment microscopy
 
Assess sCr
 
Exclude infection, trauma, bleeding from the distal urinary tract/bladder, menstruation
 
Consider bleeding disorder
 

+ Corresponds to KDIGO criteria for Acute Kidney Injury

Additional specialized assessments are available to assess renal function or renal pathology.

Whenever a renal event is identified, a detailed patient history and examination are indicated to identify and potentially eliminate risk factors that may have initiated or contributed to the event:

- Blood pressure assessment (after 5-minute rest, with an appropriate cuff size)
- Signs and symptoms like fever, headache, shortness of breath, back or abdominal pain, dysuria or hematuria, dependent or periorbital edema
- Changes in blood pressure, body weight, fluid intake, voiding pattern, or urine output
- Concomitant events or procedures such as trauma, surgical procedures, cardiac or hepatic failure, contrast media or other known nephrotoxin administration, or other diseases or causes, e.g., dehydration due to delirium, tumor lysis

**Table 16-6      Follow-up of Renal Events**

FOLLOW-UP OF RENAL EVENTS	
Assess, document and record in CRF	

• Urine dipstick and sediment microscopy evidence of DIN: crystals, red blood cells (dysmorphic/glomerular vs. non-dysmorphic/non-glomerular), white blood cells, tubular epithelial cells

• Blood pressure and body weight

• Serum creatinine, BUN, electrolytes (sodium, potassium, phosphate, calcium), bicarbonate and uric acid

• Urine output

	
Review and record possible contributing factors to the renal event (co-medications, other co-morbid conditions) and additional diagnostic procedures (MRI etc.) in the CRF	
Monitor participant regularly (frequency at investigator's discretion) until - 

• Event resolution: (sCr within 10% of baseline or PCR < 1 g/g Cr, or ACR <300 mg/g Cr) or

• Event stabilization: sCr level with <math>\pm 10\%</math> variability over last 6 months or protein-creatinine ratio stabilization at a new level with <math>\pm 50\%</math> variability over last 6 months.

• Analysis of urine markers in samples collected over the course of the DIN event

	

## 17 Cohort Specific Information

This section contains details that pertain to specific cohorts and should be considered as supplementary to information presented in the preceding core protocol sections and respective Investigator Brochures or country-specific product labels for marketed agents. If there are no cohort- or treatment-specific details presented for a given topic (e.g., cohort- or treatment-specific eligibility criteria, study restrictions, food effects, etc.), then the information in the corresponding section in the core protocol for that topic should be implemented without further adjustment.

### 17.1 Cohort 1 ACZ885

Cohort 1 will evaluate the use of canakinumab (ACZ885 or Ilaris) as an anti-inflammatory agent for the symptomatic treatment of cognition in participants with MCI due to AD or mild AD who have evidence of peripheral inflammation.

Approximately 86 participants will be randomized in a 1:1 ratio to one of the following treatment arms:

- Arm 1: canakinumab 150 mg (1 x 150 mg solution) plus matching placebo (1 x 150 mg solution) SC q 4 weeks for the first 2 doses followed by 300 mg (2 x 150 mg solution) SC q 4 weeks for the subsequent 4 doses
- Arm 2: Matching placebo

#### 17.1.1 Introduction

This treatment arm will evaluate canakinumab alone. As this treatment has an extended half-life, the EOC2 visit will serve as the end-of-study visit for participants randomized to this cohort.

**The step-up visit schedule for day 8, 15, 22, and 36, does not apply to this agent/cohort.**

#### 17.1.2 Background

Key information on canakinumab is shown in [Table 17-1](#). Please refer to sections following this table or the canakinumab and country-specific product label for additional details.

**Table 17-1 Key Information on canakinumab**

canakinumab	
Reference	IB
Drug type	Human monoclonal antibody
Half-life	26 days
Five half-lives	130 days
Generic name	Canakinumab
Formulation	Subcutaneous
Maximal planned clinical dose	300 mg q4 weeks
Target	Anti-human interleukin-1 $\beta$ (IL-1 $\beta$ ) antibody
Pharmacology	Blocks the interaction of IL-1 $\beta$ with the IL-1 receptor (IL-1R), leading to inhibition of its downstream targets, thereby preventing IL-1 $\beta$ -induced gene activation and the production of inflammatory mediators.

canakinumab	
Metabolism	Elimination pathways for the IgG-type mAbs such as canakinumab are distinct from metabolic pathways of small molecules. The IgG-based molecules are cleared from the body by a combination of processes such as proteolysis by the liver, elimination by the reticuloendothelial system (RES) and nonspecific endocytosis.
Potential to interact with other drugs based on in vitro studies	No study was conducted with canakinumab or its mouse surrogate, 1BSUR, to investigate drug-drug interaction in non-clinical species.
Reference safety information (RSI)*	System organ classes (SOCs) in the reference safety information tables as of the latest IB include infections and infestations across all indications below, in addition to the following:  CAPS: 

• Nervous system disorders

 Periodic fever syndromes 

• Investigations (platelet count decreased)

 SJIA: 

• Gastrointestinal disorders

• Immune system disorders

• Investigations (transaminases increased, platelet count decreased, neutrophil count decreased, white blood cell count decreased)

 Oncology: 

• Investigations (blood creatine phosphokinase increased)

• Blood and lymphatic system disorders

 Gouty arthritis and Cardiovascular risk reduction: 

• No additional SOCs

 Based on similarities of the patient population with Alzheimer's disease (including elderly, hypertensive, diabetes, cardiovascular disease, chronic obstructive pulmonary disease), the RSI Table 6-5 from the Cardiovascular risk reduction program (CANTOS) will be used as the RSI table for this study.
Selected safety risks†	For inflammatory indications, canakinumab is associated with an increased incidence of infections , including isolated cases of unusual or opportunistic infections (aspergillosis, atypical mycobacterial infections and herpes zoster). The majority of the events were mild to moderate, although serious infections with fatal outcome have been reported. The most frequent infections were predominantly of the upper respiratory tract. There is no significant difference in the safety profile observed in patients' $\geq 65$ years of age.

---

